7.3.4 Replacement of Subjects

A subject who withdraws from the study will not be replaced.

7.4 Treatments

The investigator will take responsibility for and will take all steps to maintain appropriate records and ensure appropriate supply, handling, storage, distribution, and use of study materials in accordance with the protocol and any applicable laws and regulations.

7.4.1 Dosage and Formulations

PN40082 (manufactured by Prollemium Medical Technologies) is a clear, colorless gel in 1.0 mL pre-filled syringes with 25 mg/mL of stabilized hyaluronic acid and lidocaine 0.3% w/w. The study device will be provided by the Sponsor.

7.4.2 Study Device Administration

All subjects in this study will receive one open-label treatment with PN40082. Subjects will maintain the unique subject number previously assigned in Protocol PRO 2018-02.

The subject should be positioned in a seated position and may be reclined to as much as 45°.

Any makeup should be removed with a gentle cleanser or a specific makeup remover product (such as Neutrogena Cleansing Makeup Remover Facial Wipes).

The non-vermillion areas of the upper and lower lips should be prepared by gentle washing with a surgical scrub product (Chlorhexidine, Technicare, etc.).

To prepare the syringes for use, the investigator should attach one of the needles included in the subject study device kit in a firm manner. The plunger should be gently depressed to express any unwanted air until a small droplet of implant material appears at the tip of the needle.

Study device is administered using only a needle provided in the subject study device kit. The needle is inserted at an approximate angle of 30° parallel to the surface of the skin or lip. For rhytids, study device should be injected into the mid-to-deep dermis. Study device should be injected into the submucosal layer for lip augmentation; care should be taken to avoid intramuscular injection. If study device is injected too superficially this may result in visible lumps and/or bluish discoloration.

Inject study device applying light to moderate, even pressure on the plunger. Avoid injecting quickly as rapid injection can result in increased pain. It is important that the injection is stopped just before the needle is pulled out of the skin to prevent material from leaking out or being too superficially implanted into the skin.

Only correct or augment to 100% of the desired volume effect. Do not overcorrect or overfill.

The needle may be replaced as needed to ensure subject comfort. Only needles provided in the subject study device kit may be used. Before needle replacement, the plunger should be withdrawn slightly and once the needle has been replaced, the plunger re-advanced to ensure that the new needle is prefilled with implant material prior to restarting injections.

Typical usage for each treatment session is specific to the site as well as the amount of augmentation or rhytids correction desired. Based on U.S. clinical studies, the maximum volume allowed per treatment is 1.5 mL per lip (1.5 for upper, 1.5 for lower) and 1.0 mL for perioral rhytid correction. Thus, the maximum amount that can be used at one treatment session is 4.0 ml.

Amounts of material injected should be recorded separately for the upper lip, lower lip and perioral areas.

INJECTION TECHNIQUES

1. Study device can be injected by a number of different techniques that depend on the treating investigator's experience and preference and subject characteristics.
2. **Serial puncture** involves multiple, closely spaced injections along wrinkles, folds, or the vermillion border. Although serial puncture allows precise placement of the filler, it produces multiple puncture wounds that may be undesirable to some subjects.
3. **Linear threading (includes retrograde and antegrade)** is accomplished by fully inserting the needle into the center of the area to be corrected or augmented and injecting the filler along the track as a "thread." Although threading is most commonly practiced after the needle has been fully inserted and is being withdrawn, it can also be performed while advancing the needle - antegrade technique). To augment the lip, the retrograde linear threading technique is the most advisable.
4. Serial threading is a technique that utilizes elements of both approaches.

Note! The correct injection technique is crucial for the final result of the treatment.

5. The following techniques should be avoided as they may result in an increase in short-term episodes of bruising, swelling, redness, pain, or tenderness at the injection site:
 - Dissection of the sub-epidermal plane with lateral movement of the needle – “fanning”
 - Rapid flow rate (> 0.3 mL/min) of implant material injection
 - High injection volumes
 - The use of needles other than ones provided in the subject study device kit
6. The use of cannulas is prohibited.
7. When the injection is completed, the treated site should be **gently** massaged so that it conforms to the contour of the surrounding tissues. Massaging that substantially deforms the lips or causes blanching of compressed tissues is excessive and should be avoided except as described below.
8. If excessive material is implanted or irregularly implanted, massage the area somewhat more firmly than for the usual implantation procedure to obtain optimal results.
9. If blanching of the tissues is observed during or directly after injection and becomes a concern, the area may be gently massaged. If blanching persists, contact the Medical Monitor.
10. The lips should be augmented to achieve the maximum desirable appearance for both the treating investigator and the subject. Subjects should be provided a small hand mirror to observe the results and further injections conducted until maximum benefit has been obtained. Care should be taken to ensure that the lips are symmetric from right to left and that the upper and lower lips have relative proportionality.
11. The perioral area should be corrected AFTER the upper and lower lips have been corrected. Some correction of perioral rhytids may occur with lip augmentation, thus it is best to address any remaining perioral correction needs after the lip injections have been completed.
12. If the treated area is swollen directly after the injection, an ice pack can be applied on the site for a short period if the investigator deems it appropriate. Ice should be used with caution if the area is still numb from anesthetic to avoid thermal injury.
13. Subjects should be encouraged to avoid a recumbent position for several hours after injections to reduce swelling. The use of ice, cold packs or other therapies to reduce swelling should only be performed at instruction of the investigator. The subject should be instructed to contact the site if substantial swelling occurs.

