14 APPENDIX 1: FILLER FIRST AID PROTOCOL (CHESTNUT C., 2018)

Materials that are needed on-site:

- Hyaluronidase (Hyalenex)
- Aspirin 325mg
- Nitroglycerin paste

Provide the following contacts to subjects and these contacts also posted on-site for easy reference:

- Ophthalmologist “on call”
- Closest ER with stroke management capability with directions to ER

Preparation:

- The above materials should be gathered and labeled for emergency use only (to ensure they are available should an urgent situation arise).
- Staff should be educated regarding the urgent nature of such an event and the location of all materials and contact information.
- Investigators may wish to familiarize themselves with the retrobulbar injection technique via literature or on line training.

It is critical to recognize any intravascular events during injections and act quickly to maximize likelihood of reversal. As soon as an intravascular is recognized, **stop any further injections**.

If a skin infarction is identified:

- Apply nitroglycerin paste – apply liberally to the affected area and massage in gently, expect headache complaint from subject but do not withhold the treatment.
- Massage area to help promoted blood flow
- Dispense Aspirin 325 mg - Have patient chew this or the aspirin may be placed sublingually for maximum rapid absorption
- If blanching persists, consider infiltration with hyaluronidase
 - Infiltrate in the area where material was being injected – this may allow hyaluronidase to enter the same vessel that was inadvertently cannulated.
 - Infiltrate in the area of blanching or ischemia as well
 - Inject a minimum of 50 units into each area; investigators are free to use larger doses as they see fit.
 - Hyaluronidase may be repeated as needed.
- Hot Packs – Towels or gel packs warmed in a microwave can be applied to the area of decreased blood flow.
- Monitor the subject and the area of blanching ischemia. If blanching persists after 24

hours,— consider hyperbaric oxygen treatments.

If signs/symptoms of visual changes, ophthalmoplegia, blindness, ocular pain (usually immediately) occur:

- Dispense Aspirin 325 mg - Have patient chew or place the tablet sublingually for maximum rapid absorption
- Massage the globe with repeated inward compression and release – this may free any embolic material
- Infiltration with hyaluronidase into area being corrected or augmented

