15 APPENDIX 2: PN40082 INSTRUCTIONS FOR USE

PN40082 Injectable Hyaluronic Acid Gel with 0.3% Lidocaine

Caution: Federal Law restricts this device to investigational use. This device is limited by Federal (or United States) law to investigational use

DESCRIPTION

PN40082 is a gel of hyaluronic acid generated by Streptococcus species of bacteria, chemically crosslinked with BDDE, stabilized and suspended in phosphate buffered saline at pH=7 with 0.3% lidocaine.

INDICATION

PN40082 is indicated for submucosal implantation for lip augmentation and dermal implantation for correction of perioral rhytids in patients over the age of 21.

CONTRAINDICATIONS

- *PN40082* is contraindicated for patients with severe allergies manifested by a history of anaphylaxis or history or presence of multiple severe allergies.
- *PN40082* contains trace amounts of gram positive bacterial proteins and is contraindicated for patients with a history of allergies to such material.
- *PN40082* is contraindicated for patients with bleeding disorders.
- *PN40082* is contraindicated for implantation in anatomical spaces other than the dermis or submucosal implantation for lip augmentation.
- *PN40082* should not be used in patients with previous hypersensitivity to local anesthetics of the amide type, such as lidocaine.

WARNINGS

- Defer use of *PN40082* at specific sites in which an active inflammatory process (skin eruptions such as cysts, pimples, rashes, or hives) or infection is present until the process has been controlled.
- Injection site reactions (e.g., lip swelling, lip pain, and contusion) to *PN40082*, including short-term minor or moderate inflammatory symptoms starting shortly after treatment of lips
- *PN40082* must not be implanted into blood vessels. Localized superficial necrosis and scarring may occur after injection in or near vessels, such as in the lips, nose, or glabellar area. It is thought to result from the injury, obstruction, or compromise of blood vessels.
- Delayed onset inflammatory papules have been reported following the use of dermal fillers. Inflammatory papules that may occur rarely should be considered and treated as a soft tissue infection.

- Injections of 4.0 mL or greater (upper and lower lip combined) per treatment session increases the occurrence of injection site reactions. If a volume of more than 3 mL is needed to achieve optimal correction, a follow-up treatment session is recommended.

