7. When the injection is completed, the treated site should be **gently** massaged so that it conforms to the contour of the surrounding tissues. Massaging that substantially deforms the lips, or causes blanching of compressed tissues, is excessive, and should be avoided except as described below.

8. If excessive material is implanted or irregularly implanted, massage the area somewhat more firmly than for the usual implantation procedure to obtain optimal results.
9. If blanching of the tissues is observed during or directly after injection, pause the procedure and massage the area gently until the color returns. If the condition persists, contact the Medical Monitor.
10. The lips should be augmented to achieve the maximum desirable appearance for both the treating investigator and the subject. Subjects should be provided a small hand mirror to observe the results and further injections conducted until maximum benefit has been obtained. Care should be taken to ensure that the lips are symmetric from right to left and that the upper and lower lips have relative proportionality.
11. The perioral area should be corrected AFTER the upper and lower lips have been corrected. Some correction of perioral rhytids may occur with lip augmentation, thus it is best to address any remaining perioral correction needs after the lip injections have been completed.
12. If the treated area is swollen directly after the injection, an ice pack can be applied on the site for a short period. Ice should be used with caution if the area is still numb from anesthetic to avoid thermal injury.
13. Subjects should be encouraged to avoid a recumbent position for several hours after injections to reduce swelling. The use of ice, cold packs or other therapies to reduce swelling should only be performed at instruction of the investigator. The subject should be instructed to contact the site if substantial swelling occurs.

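### The injection section's response to tissue blanching is conditional, optional and has no pause, so it is weaker than the protocol's own Instructions for Use

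*Protocol*

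**What the plan says.** Protocol 7.4.2 (Study Device Administration) contains a 13-item list of injection techniques. Item 9 covers blanching seen while injecting or just afterwards: "If blanching of the tissues is observed during or directly after injection and becomes a concern, the area may be gently massaged". It continues: "If blanching persists, contact the Medical Monitor".

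Appendix 2 (Instructions for Use) has a parallel 13-item list. Its item 9 starts from the same observation, without asking whether it has become a concern, and directs the injector to "pause the procedure and massage the area gently until the color returns". It then says: "If the condition persists, contact the Medical Monitor".

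Appendix 1 (Filler First Aid Protocol) states: "It is critical to recognize any intravascular events during injections and act quickly to maximize likelihood of reversal". Once such an event is recognized, its instruction is to "stop any further injections". Section 7.4.2 cites neither appendix. In the text available, Appendix 1 is cited from 7.9.3.4 (Adverse Events of Special Interest), and Appendix 2 from 7.9.6.3 as the reference for judging whether an event is expected.

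**The concern.** Blanching can be the first visible sign that filler has entered or compressed a vessel. The protocol treats that hazard as serious. The Appendix 2 warnings say: "Localized superficial necrosis and scarring may occur after injection in or near vessels, such as in the lips, nose, or glabellar area". Section 7.9.3.4 requires immediate reporting of embolic and ischemic events.

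Section 7.4.2 is the part of the protocol that governs the injection, yet it gives the weaker first response. An injector relying on it may decide that the blanching is not yet a concern. Nothing there tells the injector to pause, and massage is only permitted. Item 10, which follows directly, has the injector go on injecting until the best result is reached. Item 11 then adds perioral correction after the lips.

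What is at stake is subject safety during the session. The study is descriptive, and no efficacy or safety summary would be computed differently.

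**Working it through.** The plan states no figure on this point and no formula applies. The check sets the two instructions side by side and then looks for anything else in 7.4.2 that would close the gap.

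| Step in Appendix 2 item 9 | Protocol 7.4.2 item 9 | Result |
|---|---|---|
| Pause the procedure | Not mentioned | Absent |
| Massage gently (directed, on any blanching) | Permitted, and only once blanching is a concern | Softened |
| Continue until color returns | No end point given | Absent |
| Contact the Medical Monitor if it persists | Same instruction | Same |

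Count: 2 of 4 absent, 1 of 4 softened, 1 of 4 the same (2 + 1 + 1 = 4).

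**Is the pause supplied elsewhere in 7.4.2?** No. Nothing in the section tells the injector to pause or stop for blanching. Item 7 directs gentle massage when an injection is completed, but its purpose is contour. It also warns: "Massaging that substantially deforms the lips or causes blanching of compressed tissues is excessive and should be avoided except as described below".

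**Does 7.4.2 lead to the stronger text?** No. It contains 0 references to Appendix 1 and 0 to Appendix 2.

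**Does the pause matter for blanching seen after an injection?** Only if more injections follow in that session. That is likely to be common. Item 2 describes many closely spaced punctures, items 10 and 11 provide for further injection, and the session maximum is 1.5 + 1.5 + 1.0 = 4.0 mL over the upper lip, lower lip and perioral area.

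**Is it a contradiction?** No. A site that follows Appendix 2 also satisfies 7.4.2. The reverse does not hold: a site can satisfy 7.4.2 without pausing and so depart from Appendix 2.

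**Exposure.** There is one treatment session per subject (7.4.2), and fewer than 158 subjects are anticipated (Synopsis, Number of Subjects). No blanching rate is given, so an expected number of affected sessions cannot be calculated.

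**The case against.** The strongest reply is that the difference is small and that the dangerous case is already covered.

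- **Implied steps.** Massaging the tissue being injected implies interrupting the injection there, and a check for persistence implies the same end point as return of color. This is fair once the injector has decided to massage. It does not help when the injector judges that the blanching is not a concern, which item 9 allows.
- **Recognized events are covered.** Appendix 1 requires injection to stop and treatment to start, 7.9.3.4 requires immediate reporting, and 7.9.9 suspends the site after an embolic event leading to skin necrosis, vision loss or stroke. None of this needs a pointer in item 9. This stands, and it confines the gap to the period before an event is recognized or blanching is judged persistent.
- **The pointer goes further than the Instructions for Use.** Appendix 2 item 9 does not cite Appendix 1 either. That is correct. The added pointer is an improvement, and its absence is not a departure from the device instructions.
- **Room for judgment is reasonable.** Item 7 recognizes blanching from compression, so not all blanching is vascular. That is true, but a short pause costs little when the cause is benign, and Appendix 2 already asks for it in every case.
- **Sites have the whole protocol.** No document says that injectors use 7.4.2 without the appendices. That also stands, so the consequence depends on how sites work in practice.
- **The four-step count is not a measure of risk.** Agreed. It describes the wording only.

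**Conclusion.** The concern holds. For the same sign, 7.4.2 item 9 gives a conditional and optional response with no pause, where Appendix 2 item 9 gives a directive one. The size is two of four steps missing and one softened, over a single session per subject in an anticipated fewer than 158 subjects.

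The textual difference is certain. The practical consequence is not: it assumes that some injectors work from 7.4.2 without turning to the appendices, and that some blanching has a vascular cause. Neither frequency can be taken from the documents.

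There is a secondary ambiguity in 7.9.9. After an embolic event of the kind listed there, suspension of the whole study turns on whether the investigator properly followed the treatment SOP. That SOP is not identified in the available text, and the protocol contains two different blanching instructions. It cannot be shown that an event would be misclassified.

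The change is worth making because it alters what the injector does at the moment of risk and costs little. It has no bearing on the analysis.

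**What to change.** Replace 7.4.2 item 9 with the text of Appendix 2 item 9. On any blanching seen while injecting or just afterwards, the injector is then told to "pause the procedure and massage the area gently until the color returns", followed by "If the condition persists, contact the Medical Monitor". Add one sentence: if an intravascular event or skin infarction is recognized, "stop any further injections" and follow Appendix 1. Leave Appendix 2 as it is.

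This introduces no procedure that the protocol does not already contain. The cost is a one-item wording amendment, with documented Sponsor and IRB approval before it takes effect (Protocol 9.2 and 10.5), and a short notice to the sites. The SAP, the case report forms and the planned tables need no change on this account.

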7.4.3 Method of Packaging, Labeling, Storage, and Dispensing

For PN40082, one 1.0 mL syringe is packaged along with two fine-gauge needles (30G) in an easy-open tray. Each syringe is equipped with a Luer-Lok as well as a custom finger grip and plunger rod. The syringes contain a peelable label to be placed on the subject record for tracking purposes. Two trays are packaged in a carton. A label that includes the protocol number and Sponsor name will be attached to each carton.

All study device will be stored in a climate-controlled, limited access area.

The investigator agrees to store and administer the study device only at the site(s) listed on Form FDA 1572 (or investigator agreement/statement). The investigator, sub-investigator(s), or qualified designees also agree that the study device will be administered only to subjects who have provided written informed consent and have met all entry criteria. The study device may not be used for any purpose other than as stated in the protocol.

7.4.4 Study Device Accountability

Study device will be available on site for each subject. Receipt of study device will be documented and confirmed via the Investigational Product Receipt Form. All study device must be kept in a locked area with access restricted to designated study personnel in a climate-controlled, limited access area. The administration of study device will be recorded on the Study Device Dispensing Log. The site monitor will periodically check the supply of study device held by the investigator or pharmacist to ensure accountability. At study conclusion, all unused PN40082 study device will be returned to the Sponsor and documented using the Investigational Product Return Form.

Inventory records must be readily available for inspection by the study monitor and/or auditor, and open to inspection by regulatory authorities at any time.

7.4.5 Concomitant Medications

All medications and other treatments taken by the subject during the study are to be recorded on the CRF using their generic name, if known, with the corresponding indication. The medications to be recorded include prescription and over-the-counter (OTC) medications and dietary supplements. All medications taken on a regular basis, including vitamins, aspirin, and acetaminophen, should be recorded prior to use of the study device.

The use of any concomitant medication must relate to the subject's documented medical history, prophylaxis, or an AE.

7.4.5.1 Precautions

Subjects should be given the following additional instructions:

- Subject should minimize or avoid excessive natural or artificial sunlight exposure and extreme cold weather
- Subjects should avoid epilation, laser, mechanical or chemical peeling procedures during the study

